### 6.3. Secondary Objectives (Cohort A)

#### 6.3.1. To assess the feasibility of recruiting pediatric participants to conduct a wearable device study

- The number of participants contacted, screened and enrolled will be summarized overall and by age group. The number of participants enrolled over time (per month) for each group will be calculated and listed. The time (number of days) taken to enroll approximately 13 participants per group will be listed.

#### 6.3.2. To assess the ability of pediatric participants to perform a battery of lab-based tasks

The total number of participants able to perform each of the 7 tasks (i.e., walking at natural, slow and fast speeds, tile and carpet walks, 2 sessions of in-lab simulated activities) will be summarized overall and by age group. The number of tasks performed by each participant (out of a total of 7 tasks) will be derived and expressed as a percentage. Descriptive statistics of this percentage across participants will be computed.

#### 6.3.3. To assess the compliance in wearing the ActiGraph devices at home

Compliance information for at-home deployment will be based on wear time derived from both wrist and lumbar-worn ActiGraph device. First and last day will be removed for this analysis as we do not expect whole 24 hours of data.

For the wrist device, for each participant, the (a) *Wrist wear time*: Number of hours per day wearing the wrist device; (b) *Wrist compliant days*: Number of days with more than 18 hours of wrist wear time will be derived. Wear time will be obtained from the manufacturer's default parameter (Wear).

For the lumbar device, for each participant, the (a) *Lumbar wear time*: Number of hours per day wearing the lumbar device; (b) *Lumbar compliant days*: Number of days with more than 10 hours of lumbar wear time will be derived. Wear time will be obtained from the manufacturer's default parameter (Wear).

Summary statistics will be computed for these four endpoints across all participants and by age group. Box and whiskers plots of *wear time per day* (in hours and percentage of the day) across participants will be provided for both wrist and lumbar sensors.

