
To assess the ability of pediatric participants to perform a battery of lab-based tasks.	
Number of participants (overall and per age group) able to perform each of the 7 tasks and task-completion percentage (among total of 7 tasks) per participant.

To assess the compliance in wearing the ActiGraph devices at home.	
Number of hours per day wearing the device and number of days with more than 10 hours of wearing time for each participant.

To evaluate the participant's or caregiver's perception of wearability and comfort of ActiGraph and APDM devices during in-lab sessions.	
In-lab ActiGraph/APDM wearability/comfort questionnaire responses from Visit 1 (Day 1).

 To evaluate the participant's or caregiver's perception of wearability and comfort of ActiGraph devices during the at-home monitoring period. 	
 At-home ActiGraph wearability/comfort questionnaire responses from at-home monitoring period in the Final Study Evaluation (Day 15 + 3 days).

 To evaluate the effect of floor surface (carpet vs tile) on gait metrics collected using ActiGraph and APDM devices. 	
 Gait metrics defined in the Annex 2 (eg, gait speed, stride length) measured by ActiGraph and APDM devices across different floor surfaces.
Tertiary/Exploratory Objective(s):	Tertiary/Exploratory Endpoint(s):

 To investigate the feasibility of using a daily activity diary to provide context in pediatric physical activity data collected by ActiGraph devices at home in pediatric participants. 	
 Daily activity diary responses and metrics related to physical activity endpoints from ActiGraph (eg, sedentary time as defined in Annex 3).

 To compare gait speed collected using the SIMI system and GAITRite® walkway, during in-lab sessions. 	
 Gait speed defined in the Annex 2 measured by SIMI system and GAITRite® walkway.

COHORT B: Panoramic Bracelet Device

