5. Participants who self-report any medical condition (including pregnancy) and/or medication use, or in the investigator's opinion, any medical or psychiatric condition, and/or use of medications such as but not limited to antipsychotics, hallucinogens, amphetamines, barbiturates, etc, that may affect the safety of the participant and may interfere with the conduct of the study.
6. Other medical or psychiatric condition that may increase the risk of study participation or, in the investigator's judgment, make the participant inappropriate for the study.
7. Participants with known allergies to components as specified by device manufacturer if applicable (eg, plastic, stainless steel and silicone).

Variables

The study will enroll pediatric qualified participants at a single center in Cambridge, MA. Potential confounding variables including age, gender and race will be assessed at the start of

study procedures and be adjusted for as necessary in the statistical analysis, as noted in the Statistical Analysis Plan (SAP) and **DATA ANALYSIS** Section.

The following variables will be measured for each age group:

- Gait metrics defined in [Annex 2](#) (eg, gait speed, stride length) measured by APDM devices and GAITRite® walkway, device under study, SIMI system and GENEActiv (for Cohort B only)
- Measures of the recruitment: number of participants contacted, screened and enrolled over time, time to enroll approximately 13 participants per group, mean number of participants recruited per month (overall and per group).
- Measures of the ability to perform a battery of lab-based tasks: number of participants (overall and per age group) able to perform each of the 8 tasks and task-completion percentage (among total of 8 tasks) per participant.
- Measures of the compliance in wearing device under study at-home: number of hours per day wearing the device and number of days (>10 hours per day) wearing the device for each participant.
- Measures of the perception of wearability/comfort of the device under study and APDM (Cohort A only) devices: wearability/comfort questionnaires answers.
- Daily activity diary answers. (Only Cohort A)
- Daily activity and sleep diary answers Only Cohort B)
- Physical activity endpoints from devices under study (eg, sedentary time, sleep as defined in [Annex 3](#))

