Number of hours per day wearing the device and number of days with more than 10 hours of wearing for each participant will be recorded. Summary statistics will be provided for both endpoints for all participants and by age groups.

4. To evaluate the participant's or caregiver's perception of wearability and comfort of ActiGraph and APDM devices during in-lab sessions.

The wearability/comfort questionnaire for the in-lab session will be summarized by frequency and percentages. The study will further compare participant reported wearability and comfort from the exit questionnaire amongst locations (wrist and lumbar) using Wilcoxon signed rank test.

5. To evaluate the participant's or caregiver's perception of wearability and comfort of ActiGraph devices during the at-home monitoring period.

The wearability/comfort questionnaire during the at home period (Day 15+3 days) will be summarized by frequency and percentages. This study will compare responses from each of questionnaire amongst locations (wrist and lumbar) using Wilcoxon signed rank test.

6. To evaluate the effect of floor surface (carpet vs tile) on gait metrics collected using ActiGraph and APDM devices.

This study will quantify differences between sensor-derived gait quality metrics (from ActiGraph and APDM) collected on different floor surfaces using paired tests (t-test or Wilcoxon signed ranks test depending on normality of the data).

Tertiary/Exploratory objectives

1. To investigate the feasibility of using a daily activity diary to provide context in pediatric physical activity data collected by ActiGraph devices at home in pediatric participants. Mixed effects model with repeated measurement, ie, MMRM will be utilized to examine the association between ActiGraph measured activity metrics and participants' responses from the daily activity diaries across the whole at-home monitoring period.
2. To compare gait speed collected using the SIMI system and GAITRite® walkway, during in-lab sessions.

Accuracy of the measurements of gait speed will be determined by computing the mean absolute percent error between SIMI system and GAITRite® walkway and assess the bias using Bland-Altman plots and 95% limits of agreement. The agreement between SIMI system and GAITRite® walkway will be assed using ICC and its lower and upper limits.

COHORT B:

Primary Objectives

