## 3.2. Secondary Endpoints

**Table 4. Secondary Objectives and Endpoints (Cohort A)**

Secondary Objective(s):	Secondary Endpoint(s):

 
• To assess the feasibility of recruiting pediatric participants to conduct a wearable device study.
 
	
 
• Recruitment data listed by age group:           
 
(a) Number of participants contacted
 
(b) Number of participants screened
 
(c) Number of participants enrolled over time
 
(d) Time taken (number of days) to enroll approximately 13 participants per group
 
 
 

 
• To assess the ability of pediatric participants to perform a battery of lab-based tasks.
 
	
 
• Total number of participants able to perform each of the 7 tasks
 
• Number of participants per age group able to perform each of the 7 tasks
 
• Percentage of tasks completed (from a total of 7 tasks)
 

 
• To assess the compliance in wearing the ActiGraph devices at home.
 
	
 
• Number of hours per day wearing the lumbar and wrist devices
 
• Number of days with more than 10 hours of wear time for lumbar device
 
• Number of days with more than 18 hours of wear time for wrist device
 

 
• To evaluate the participant's or caregiver's perception of wearability and comfort of ActiGraph and APDM devices during in-lab sessions.
 
	
 
• Wearability/Comfort Questionnaire for APDM device and for Actigraph lumbar and wrist device separately (All questions are on a 5-point Likert scale)
 
• Cognitive Debrief of Wearability/Comfort Questionnaire
 

 
To evaluate the participant's or caregiver's perception of wearability and comfort of ActiGraph devices during the at-home monitoring period.
 
	
 
Wearability/Comfort Questionnaire for Actigraph lumbar and wrist device separately (All questions are on a 5-point Likert scale)
 

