#### 6.4. Secondary Objectives (Cohort B)

##### 6.4.1. To assess the compliance in wearing the Panoramic Bracelet device at home.

Compliance information for at-home deployment (~Days 1-7) will be based on wear time parameters (Section 3.1.2.3) derived from the Panoramic Bracelet device. First and last day may be removed for this analysis as we do not expect whole 24 hours of data.

Summary statistics will be computed for the wear endpoints across all participants and by age group. Box and whiskers plots (in hours and percentage of the day) across participants will be provided.

Two definitions of compliant days will be derived: 1) >10 hours of wear time, and 2) >18 hours of wear time per day. The summary statistics will be presented in a table.

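### Cohort A wrist wear: the protocol counts days above 10 hours, the SAP counts only days above 18 hours, and the change is not explained

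*SAP*

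**What the plan says.** The protocol states the Cohort A day count three times, each time at 10 hours and without reference to body location:

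- Research Question and Objectives, Cohort A secondary endpoints: "Number of hours per day wearing the device and number of days with more than 10 hours of wearing time for each participant".
- Variables, for the device under study at home: "number of hours per day wearing the device and number of days (>10 hours per day) wearing the device for each participant".
- Statistical Analysis, Cohort A secondary objective 3: "Number of hours per day wearing the device and number of days with more than 10 hours of wearing for each participant will be recorded".

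Two ActiGraphs go home with each Cohort A child, one on the non-dominant wrist and one on the lumbar region. Under At-home Monitoring, the wrist device is to be worn without a break, while the lumbar device comes off for night sleep and naps.

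The SAP splits the count by location. Table 4 lists "Number of days with more than 10 hours of wear time for lumbar device" and, separately, "Number of days with more than 18 hours of wear time for wrist device". Section 6.3.3 repeats the split: "Number of days with more than 10 hours of lumbar wear time will be derived" for the lumbar device and "Number of days with more than 18 hours of wrist wear time will be derived" for the wrist. It also derives daily wear hours for both devices, summarises all four measures overall and by age group, and box-plots daily wear. No reason is given for 18 hours.

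For the Cohort B wrist device, SAP 6.4.1 uses both cut-offs: "Two definitions of compliant days will be derived: 1) >10 hours of wear time, and 2) >18 hours of wear time per day".

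**The concern.** A wrist-day count that the protocol defines has been replaced by a different one under the same objective, and nothing in either document says why. The cut-off alone decides whether a day counts, and the range between 10 and 18 hours is where a day without overnight wear would usually fall. A reader with the protocol in hand would expect a wrist count at 10 hours and find one at 18. The two numbers could differ widely for the same child.

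The protocol's rationale names compliance data for planning later paediatric studies as a product of this study. A wrist compliance figure that depends on an unexplained cut-off is harder to carry into that planning. In addition, the 10-hour wrist count will exist for Cohort B and not for Cohort A, although both cohorts wear the device on the same wrist, under the same continuous-wear instruction and in the same age bands.

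**Working it through.** Neither cut-off is derived from other figures, so there is no stated result to reproduce. The check compares the two rules directly.

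**Inputs**
- Protocol cut-off: more than 10 h per day (endpoint table, Variables, Statistical Analysis).
- SAP wrist cut-off: more than 18 h per day (Table 4, 6.3.3).
- Days analysed: SAP 6.3.3 drops the first and last day. If Day 15 is the last day, Days 2 to 14 remain: 14 − 2 + 1 = 13 days.
- Length of overnight removal: not given in the documents, so it is varied as an assumption.

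**Where the rules part**
- As a share of the day: 10/24 = 41.7% and 18/24 = 75%.
- Wear = 24 − hours off. Wear above 18 h means less than 24 − 18 = 6 h off. Wear above 10 h means less than 24 − 10 = 14 h off.
- The rules therefore disagree when the device is off for at least 6 h and under 14 h, that is, for wear above 10 h and up to 18 h. Outside that band they agree.

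**A child with the same hours off every day, 13 days analysed**

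| Hours off | Wear (h) | Days counted at >10 h | Days counted at >18 h |
|---|---|---|---|
| 5 | 19 | 13 | 13 |
| 6 | 18 | 13 | 0 |
| 8 | 16 | 13 | 0 |
| 10 | 14 | 13 | 0 |
| 12 | 12 | 13 | 0 |
| 13 | 11 | 13 | 0 |
| 14 | 10 | 0 | 0 |

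For a child who leaves the device off for 8 to 12 h on k of the 13 days and for under 6 h on the others, the counts are 13 at 10 h and 13 − k at 18 h. The gap equals the number of such days, so any percentage quoted for a cohort only restates the removal rate that was assumed.

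**What is and is not planned for the Cohort A wrist**
- Hours per day: planned.
- Days above 18 h: planned.
- Days above 10 h: not planned. The same count is planned for the Cohort A lumbar device and for the Cohort B wrist device.

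**The case against.** The case for the SAP is substantial, and most of it stands.

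- **The split fits the wear instructions.** The wrist device should stay on day and night and the lumbar device only while the child is awake. A 10-hour count for the wrist would register almost no overnight removal, and an 18-hour count would. The protocol's single cut-off did not deal with two devices worn on different schedules.
- **The change is allowed.** The protocol's Data Analysis section and SAP Section 2 let the SAP alter planned analyses, and they call for an amendment only for major changes to primary endpoints. This endpoint is secondary and descriptive.
- **Little information is lost.** Daily wrist hours are reported with box plots, and the missing count can be derived from them. The 18-hour wrist count exists in both cohorts, so they can be compared on it.

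A reader might infer that the protocol's compliance endpoint goes unreported altogether. It does not: hours per day are reported for both devices and the 10-hour count is kept for the lumbar one. A reader might also infer that the SAP's version history hides a change. That table logs changes between SAP versions. If 18 hours was already in version 1, there was nothing to log, and the documents do not show otherwise. Nor would a 10-hour count by itself separate daytime from overnight wear, since neither cut-off records the time of day.

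These points do not supply the missing explanation, and hour summaries and box plots do not give each child's number of days above 10 hours, which is what the protocol specifies.

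**Conclusion.** The discrepancy is real and narrow. For the Cohort A wrist device, the protocol's count of days above 10 hours is replaced by a count above 18 hours without a stated reason, while the Cohort B wrist device gets both. The classification arithmetic is exact: every wrist day with more than 10 and up to 18 hours of wear changes class. The example of 13 of 13 days against 0 of 13 rests on two assumptions: removal for 8 to 12 hours every night, and Day 15 as the last day. How often such days will occur cannot be known from the documents.

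The 18-hour cut-off is itself defensible. This is an unexplained departure in a descriptive secondary endpoint, not a breach of the protocol. The primary gait comparison, the sample size and the hypothesis tests are unaffected.

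**What to change.** In SAP Table 4 and Section 6.3.3, report Cohort A wrist days at both cut-offs: above 10 hours, labelled as the protocol endpoint, and above 18 hours, labelled as a measure of continuous wear. This follows what 6.4.1 already does for Cohort B. Add one sentence saying why 18 hours is used for the wrist.

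The cost is one more derived variable and one more table row, from wear hours that the SAP already computes. No new data are needed, and only SAP wording changes.

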#### 6.3.4. To evaluate the participant's or caregiver's perception of wearability and comfort of ActiGraph and APDM devices during in-lab sessions

The Wearability/Comfort Questionnaire responses from the in-lab visit (Day 1) for the APDM device and for the Actigraph lumbar and wrist devices will be summarized as frequency and percentages. Bar plots will be provided per question.

Participant responses for Actigraph wrist and lumbar devices will be compared to assess the participants' preference for device location. Due to the ordinal nature of the responses, a 0 to

4 scale will be assigned to each option (i.e. 0 = strongly disagree, and 4 = strongly agree), except for questions 5 (“The device changes the way I move”) and 6 (“The device changes the way I behave”), where the order of the scale should be reversed (i.e. 0 = strongly agree, and 4 = strongly disagree) to be consistent with the ranking of other questions. The total score will be calculated by summing up numeric scales for each individual question. Wilcoxon signed rank test will be used to test the paired difference of total score between wrist and lumbar. A non-significant result would indicate that there is no evidence of a systematic difference between the wearability and comfort of wrist and lumbar locations, while a significant result would indicate the presence of systematic differences between the two locations. Results will be presented in a table.

The Cognitive Debrief of Wearability/Comfort Questionnaire will be summarized as frequency and percentages when appropriate. Participant explanations entered as free text will be provided in a listing.

### **6.3.5. To evaluate the participant’s or caregiver’s perception of wearability and comfort of ActiGraph devices during the at -home monitoring period.**

The Wearability/Comfort Questionnaire responses obtained during the Final Study Evaluation (Day 15 + 3 days) for the Actigraph lumbar and wrist devices will be summarized as frequency and percentages. Bar plots will be provided per question.

Participant responses for Actigraph wrist and lumbar devices will be compared and presented as described in Section 6.3.4.

### **6.3.6. To evaluate the effect of floor surface (carpet vs. tile) on gait metrics collected using ActiGraph and APDM devices.**

The effect of floor surface will be evaluated on gait metrics extracted from APDM and Actigraph worn on the lumbar position (Section 3.2., Table 4).

The following analyses and plots will be provided (see Table 10):

- Box and whiskers plots of gait parameters by floor type.
- The effect of floor type on gait parameters will be analyzed using paired tests (paired t-test or Wilcoxon Signed-rank test), and the effect size will be computed per device.
- Mixed model regression analyses will be used to investigate the effect of device (APDM vs Actigraph), and device by floor type (carpet vs tile) interaction. The device, floor type, and their interaction will be fixed effects, and subject will be entered as random effect. Post-hoc t-tests might be performed between devices. Multiple comparisons, when necessary, will be performed using FDR. Age (or age group) and sex may be used as covariates in the model. The estimates for fixed effect parameters, standard errors, 95% CIs, and p-values, as well as the variance estimates for the random effect will be summarized. Results from all models will be presented in a table. Furthermore, Least Squares Means (LSMeans) together with their 95% CI will be calculated for each device-floor-type combination.

**Table 10. Specific Endpoints for Secondary Objective (Cohort A): Evaluation of floor surface effect**

Task	Devices	Measurements/comparisons
In-lab walk on tile and carpet on natural speed	Reference: APDM Comparator: Actigraph-lumbar (gaitPy)	Gait metrics (Comparison within and between devices)

#### 6.4. Secondary Objectives (Cohort B)

##### 6.4.1. To assess the compliance in wearing the Panoramic Bracelet device at home.

Compliance information for at-home deployment (~Days 1-7) will be based on wear time parameters (Section 3.1.2.3) derived from the Panoramic Bracelet device. First and last day may be removed for this analysis as we do not expect whole 24 hours of data.

Summary statistics will be computed for the wear endpoints across all participants and by age group. Box and whiskers plots (in hours and percentage of the day) across participants will be provided.

Two definitions of compliant days will be derived: 1) >10 hours of wear time, and 2) >18 hours of wear time per day. The summary statistics will be presented in a table.

##### 6.4.2. To compare gait quality metrics collected using Panoramic Bracelet devices, APDM devices and GAITRite® walkway, during in-lab sessions.

The common endpoints are derived from the Panoramic Bracelet device with respect to GAITRite and APDM. Same analyses plan will be implemented as listed in Section 6.1 Primary Objective (Cohort A).

Additionally, Deming regression will be used to assess relationship of endpoints between the comparator and reference devices while taking into account of variations from the multiple measures. The fitted slope, intercept and their corresponding 95% CI will be reported. Weighted Deming and Passing-Bablok regression may also be considered if deemed appropriate.

